To properly estimate the number of patients that will belong to this w8-w32 insufficient responder group (target of LDA: DAS28CRP \leq 3.2), data from the previous CareRA trial were used, in which ‘COBRA-Slim’ was compared with other remission induction schemes (Verschueren et al, 2015). In the CareRA trial population around 25% of patients required a second treatment adaptation because they did not reach LDA during the remission induction phase after a first adaptation of MTX dose increase to 20 mg.

Expected difference in effect

The early insufficient responders in the previous CareRA trial had a mean AUC under the DAS28CRP curve of 351.3 (SD 103) after 2 years. We estimate that patients in this insufficient responder group, when given the opportunity to have accelerated access to a short course of etanercept, will have an increase in effect size, reflected by a decrease in AUC at w104 in comparison to the reference arm. We consider a 20% decrease in AUC (from 351 to 281) to be clinically relevant and assume the same standard deviation. A 20% reduction in AUC over the first 104 weeks of treatment would reflect an important decrease of the overall disease burden. Additionally, we believe that this is the minimum effect size to consider an early access to anti-TNF to be cost-effective.

Sample size calculation of insufficient responders

For a superiority design, with a two-sided alpha of 0.05, the null and alternative hypotheses are:

- **Null hypothesis:** In early insufficient responders to COBRA-Slim induction therapy, accelerated access to anti-TNF therapy leads to the same AUC compared to treatment

adaptation according to the standard COBRA-Slim strategy after 104 weeks (there is no difference in AUC in early insufficient responders). $H0: \delta = 0$

- **Alternative hypothesis:** In early insufficient responders to COBRA-Slim induction therapy, accelerated access to anti-TNF therapy can be considered as superior to the standard COBRA-Slim strategy. $H1: \delta \neq 0$

These are the parameters taken into account for the sample size calculation, using PASS 14 software (PASS 14 Power Analysis and Sample Size Software, 2015. NCSS, LLC. Kaysville, Utah, USA, ncss.com/software/pass):

- Calculation of Superiority / Test for Two means (likelihood ratio test).
- Allocation of 1:1
- Power of 0.80
- α was set at 0.05.

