- Primary endpoint is AUC after 104 weeks in early insufficient responders, with a mean AUC of 351 (SD 103) after 104 weeks in the reference group following the traditional COBRA-Slim adaptation strategy, as estimated based on data from the CareRA trial.
- Assumed 20% lower mean AUC after 104 weeks (281 (SD 103)) in the arm with accelerated access to etanercept.

To achieve a power of 80%, 70 insufficient responders have to be randomized. Based on the CareRA data we expect a 21% dropout rate up until week 104. Therefore, we aim to randomize 90 insufficient responders. As mentioned above, the insufficient responders are expected to represent 25% of the total population of the trial. After adjusting for the expected 6% screen/randomization failures, we expect that 383 patients have to be screened for the new CareRA2020 trial in order to randomize 90 insufficient responders. The 6% expected screen/randomization failures is based on CareRA data, showing 21 failures out of 400 patients.

Increasing the sample size would help to account for possible influence of missing data on the statistical power to detect the estimated difference in effectiveness of the remission induction schemes (Little et al, 2012) and allow us to perform a statistically more robust exploration of the secondary endpoints. Realistically, a sample size of around 440 patients is feasible in practice (see planned recruitment rate), which would lead to the randomization of 104 patients, of which 82 would not drop out. This would yield 86% power.

Table: Sample size calculation for primary endpoint

N screened	N entered (assuming 6% screening failures)	N insufficient responders (assuming 25%)	N complete insufficient responders (assuming 21% dropout)	Power
383	360	90	70	80%
442	416	104	82	86%

Planned recruitment rate

Every effort will be made to gather a representative sample of patients, reflecting a normal distribution of an early RA population in Belgium. In order to achieve this, it is aimed for to propose all early RA patients who are newly or recently diagnosed at the participating centers, to take part in this trial. In- and exclusion criteria are not too restrictive towards patient recruitment. This means that all csDMARD naive patients, recently diagnosed with RA, can be included unless there are contra indications towards the proposed treatment strategy.

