Area under the curve of DAS28CRP over 104 weeks (long term effectiveness) in insufficient responders (w8-w32) randomized to either COBRA-Slim Bio-Induction or Standard COBRA-Slim Induction.

Method of analysis

Because missing data are expected, we will use the method from Bell et al to compare AUC between treatment arms based on a mixed model for repeated measures (MMRM) with DAS28CRP as the outcome (Bell et al, 2014). The model will be adjusted for the variables used in the minimization algorithm for treatment assignment (moment of randomization; between w8 and w32 but preferably at the dedicated time points w8, w16, w24, or w32 from baseline), DAS28CRP at baseline, and RF/ACPA status (see table). The effect of treatment arm is corrected for minimization factors to obtain correct P values and confidence intervals and to avoid an unnecessary loss in power (Kahan & Morris, BMJ 2012). The model will include the following mandatory visits: w4, w8, w16, w24, w32, w40, w52, w64, w78, w91, and w104.

Table: Minimization variables.

Variable	Description
Timing of randomization	Randomization is possible between w8 and w32 preferably at the dedicated time points (w8, w16, w24, w32)
Disease activity at baseline	DAS28CRP score categorized as low (≤ 3.2), moderate (> 3.2 to ≤ 5.1), or high (> 5.1).
RF and/or ACPA status	Positive serology of either RF or ACPA versus negative serology for both

We will report the estimated difference in AUC between study arms together with a 95% confidence interval. The confidence interval mainly helps to interpret the uncertainty around the treatment effect, but it can also reveal whether the treatment effect is statistically significant at the 5% level.

Plans for handling multiple comparisons, missing data, non-compliers, spurious data and withdrawals in analysis

Missing values for the primary endpoint may arise because not all measurements to derive the presence of remission are available, or because patients withdraw from the study. We expect around 21% dropouts based on the CareRA trial. Most will be lost to follow-up or due to patient withdrawal; occasionally patients drop out because of death or logistic reasons (Verschueren et al, 2016).

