11% at that stage in the trial, based on the CareRA data, this main secondary outcome will have sufficient power under the assumption that remission rate is 50% in the standard COBRA-Slim arm vs 80% in the experimental arm (table).

Table: Sample size calculation for main secondary endpoint

N screened	N entered (assuming 6% screening failures)	N insufficient responders (assuming 25%)	N complete insufficient responders (assuming 11% dropout)	Power
383	360	90	80	82%
442	416	104	92	87%

Assuming the MAR assumption of missing values, we plan to analyse the main secondary outcome measure with MMRM that is adapted for binary outcomes (O'Kelly & Ratitch, 2014). The model will be adjusted for the variables used in the minimization algorithm for treatment assignment (moment of randomization; i.e. w8, w16, w24, or w32 from baseline), DAS28CRP at baseline, and RF/ACPA status. For every participant, remission is measured at five visits up to week 28 after randomization: the randomization visit (RV), RV plus 4/8 weeks, RV plus 12/16 weeks, RV plus 20/24 weeks, and RV plus 28 weeks (Table 4).

Table 4.

Randomization visit (RV)	Weeks since baseline							
	8	16	W24	W32	W36	W44	W52	W60
W8	×	×	×	×	×			
	(RV+0w)	(RV+8w)	(RV+16w)	(RV+24w)	(RV+28w)			
W16		×	×	×	×	×		
		(RV+0w)	(RV+8w)	(RV+16w)	(RV+24w)	(RV+28w)		
W24			×	×	×	×	×	
			(RV+0w)	(RV+8w)	(RV+16w)	(RV+24w)	(RV+28w)	
W32				×	×	×	×	×
				(RV+0w)	(RV+8w)	(RV+16w)	(RV+24w)	(RV+28w)

All other secondary outcomes are to be considered as explorative. We will therefore report effect sizes with 95% confidence intervals. These confidence intervals will only be used to interpret the uncertainty around the effect size, not to determine statistical significance.

All secondary outcomes measures are clearly described under section 2 objectives and outcome measures/endpoints.

Subgroup analyses

Treatment response heterogeneity could be explored by adding a possible influencing factor and its interaction term with the treatment arm into the same linear regression model made for the first sensitivity analysis of the primary endpoint (Lagakos, 2006; Gabler et al, 2009). This method of analysis could suggest the effect of this factor on the treatment response.

Adjusted analysis

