- Use of an Interactive Web Response System (IWRS) that will be integrated into the CRF: When a randomization procedure becomes mandatory, a pop-up will appear in the CRF and an email will be sent to the investigator of the site and the project manager of the trial. The investigator will be able to randomize the subject in the same web platform via the integrated IWRS. This should help the investigator to efficiently randomize the subject and to avoid errors or forgetfulness.

Follow-up after Treatment Discontinuation:

- When study treatment is discontinued, every effort will be made to continue the follow up of the patients with their consent for collection of data on alternative treatments and outcomes. This will preserve the ability to analyze end points for all participants who underwent randomization. It also allows exploration of whether the assigned therapy affected the use and efficacy of subsequent therapies and provides the ability to monitor side effects that might occur or persist after the discontinuation of treatment. (Little et al, 2012).
- When a patient withdraws or is withdrawn from the study, regardless of the reason, the date of withdrawal and the reason for termination will be documented on a withdrawal/trial completion page.
- Every effort should be made to determine the reason why patients fail to return for the necessary visits or withdraw from the study.

Other statistical considerations.

We will focus on effect sizes and confidence intervals in the statistical analysis of this trial. Only for the analysis of the primary endpoint and the main secondary endpoint statistical significance at the 5% alpha level will be determined.

No deviations from the current statistical plan are foreseen and in case this would be needed at a later stage, an amendment to the protocol will be submitted

Economic evaluation

Depending on the clinical results of the trial, a health economic analysis may be justified. This could be part of a health technology assessment project at KCE. Quality of life (EQ5D) data, information on professional and vocational participation (Work Productivity and Activity Impairment (WPAI) questionnaire) as well as the national number of the participating patients are collected in this trial to facilitate a possible economic analysis.

11 Data handling

Data collection tools and source document identification

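### The primary AUC test is held at 5%, but remission 28 weeks after randomization is also tested at an unconditional 5%, with no rule linking the two tests

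*Combined protocol and SAP*

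**What the plan says.** The sample size section sets up the primary comparison: "For a superiority design, with a two-sided alpha of 0.05, the null and alternative hypotheses are". The hypotheses that follow concern AUC only. The primary outcome analysis adds that, besides showing uncertainty, the confidence interval matters because "it can also reveal whether the treatment effect is statistically significant at the 5% level".

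A later subsection of the primary outcome analysis is headed "Plans for handling multiple comparisons, missing data, non-compliers, spurious data and withdrawals in analysis". Its text deals with missing values, dropout, multiple imputation and a missing-not-at-random sensitivity analysis. It says nothing about multiple comparisons.

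The secondary outcome analysis gives the main secondary endpoint (remission 28 weeks after randomization) its own power table. It then sets the remaining outcomes apart: "All other secondary outcomes are to be considered as explorative". Their intervals are not to be used to judge significance.

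Other statistical considerations states the testing rule: "Only for the analysis of the primary endpoint and the main secondary endpoint statistical significance at the 5% alpha level will be determined". No section says whether the second test depends on the first.

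**The concern.** The plan deliberately treats remission as an inferential endpoint alongside AUC, rather than with the descriptive outcomes. Read literally, a non-significant AUC and a remission result with p below 0.05 would allow the remission result to be declared statistically significant, with no allowance for its being the second of two tests.

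The two endpoints answer different questions: long-term effectiveness over 104 weeks, and short-term efficacy shortly after a 24-week etanercept course. They could therefore disagree. The trial is open label, so how a split result may be claimed is best settled before outcome data are examined.

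**Working it through.** **Inputs from the documents**
- Tests: two endpoints, each at 5%. AUC is stated as two-sided. Two-sided is assumed for remission, and the stated power agrees with that.
- AUC: "with a mean AUC of 351 (SD 103) after 104 weeks in the reference group", against an assumed 281 with the same SD, so a difference of 351 − 281 = 70. Allocation is 1:1. Completers are 70 (35 per arm, stated power 80%) or 82 (41 per arm, stated power 86%).
- Remission: 50% against 80%. Completers are 80 (40 per arm, stated power 82%) or 92 (46 per arm, stated power 87%).

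**Assumption:** the correlation ρ between the two test statistics is not in the documents, so a range is shown.

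**Step 1: is an alpha split already built into the stated power?**

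For AUC, a two-sided two-sample t test has noncentrality 70 / (103 × √(2/n)).
- n = 35: 70 / 24.62 = 2.84 on 68 df, power 80.0%.
- n = 41: 70 / 22.75 = 3.08 on 80 df, power 86.0%.

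For remission, the pooled formula without continuity correction gives power Φ[(0.30 − 1.96 × √(2 × 0.65 × 0.35/n)) / √((0.25 + 0.16)/n)].
- n = 46: (0.30 − 1.96 × 0.0995) / 0.0944 = 1.113, power 86.7%.
- n = 40: power 81.6%.

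All four stated figures reproduce at the full 5%. At 2.5% each, the planned size would give 78.4% for AUC and 79.3% for remission. No split is built in.

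**Step 2: error rates if both nulls are true**

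The chance of at least one significant result is 1 − P(|Z₁| < 1.96 and |Z₂| < 1.96), with (Z₁, Z₂) bivariate normal with correlation ρ. At ρ = 0 this is 1 − 0.95² = 9.75%. The excess over 5% is the chance that remission is significant while AUC is not. The last column counts only false claims of benefit: 1 − P(Z₁ < 1.96 and Z₂ < 1.96).

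| ρ (assumed) | At least one false result | Excess over 5% | False benefit only (one test: 2.5%) |
|---|---|---|---|
| 0 | 9.75% | 4.75% | 4.9% |
| 0.3 | 9.5% | 4.5% | 4.8% |
| 0.5 | 9.1% | 4.1% | 4.5% |
| 0.75 | 8.1% | 3.1% | 4.0% |
| 0.8 | 7.8% | 2.8% | 3.9% |
| 0.9 | 7.0% | 2.0% | 3.5% |

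If only one null is true, only that test can produce a false result, and the rate is 5%.

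**Step 3: the same under a fixed sequence**

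- AUC null true, whatever the truth for remission: a false claim first needs a significant AUC result, so the rate is 5%.
- Only the remission null true: a false remission claim needs both tests significant, so the rate is at most 5%.

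The chance of both claims under the planned effects, with powers of 86.0% and 86.7%, is 0.860 × 0.867 = 74.6% at ρ = 0. It is about 80% at ρ = 0.7 and about 82% at ρ = 0.9.

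**The case against.** A ranking of endpoints already exists. AUC is the single primary endpoint, it alone has formal hypotheses, and it sets the sample size; remission is called secondary throughout. The plan also restrains multiplicity: it limits significance decisions to two prespecified endpoints, and it says that effect sizes and intervals are the main focus. The dissemination policy asks for unbiased reporting that takes the primary endpoint into account. Whether a single named secondary endpoint in a pragmatic strategy trial must be conditional on the primary is partly convention.

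Much of this stands. The primary test's error rate is unaffected. The 8 to 10% range needs both nulls to be true and counts errors in either direction. Its upper end needs near independence, which is unlikely for two measures derived from DAS28CRP in the same patients.

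Three stronger readings are tempting, and the documents support none of them:
- A reader might infer that remission gives the trial a second route to a positive conclusion. No section says that a significant secondary result makes the trial positive.
- A reader might infer that remission is the easier endpoint to win because it is measured soon after the etanercept course. The planned powers are 86% and 87%, so the plan's own assumptions give it no real advantage.
- A reader might use the 8 to 10% to describe a trial in which etanercept truly improves remission but not AUC. In that case the remission result is correct, and the only possible false claim is on AUC, at 5%.

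The objection does not supply the missing rule. The labels rank importance, but they do not make the second test conditional on the first.

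**Conclusion.** The point holds as a gap in the testing rule. It is not a fault in the primary inference. The AUC test is protected at 5%; a significance claim for remission made when AUC is not significant is unprotected.

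If both nulls are true, the chance of at least one false significant result is about 8 to 10% for assumed correlations of 0 to about 0.75, and 7.0% at 0.9. For false claims of benefit alone it is about 4 to 5% against 2.5%, over the same range of 0 to about 0.75. These figures assume bivariate normal test statistics and a two-sided 5% level for both tests.

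The sample size, stated powers, estimates and intervals need no correction. This is a cheap improvement worth making, because the plan's own heading promises a rule that it does not give.

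**What to change.** Under the heading that announces multiple comparisons, and again in Other statistical considerations, state a fixed sequence:
- Test AUC at two-sided 5%.
- Test remission 28 weeks after randomization at two-sided 5% only if AUC is significant.
- Otherwise report remission as an estimate with a 95% confidence interval, without a significance claim, as is already planned for the other secondary outcomes.

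The text is one sentence in each place. The plan itself requires changes to the statistical plan to go through a protocol amendment.

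The number of patients and the primary power (86%) do not change. The price is that no formal remission claim is possible if AUC fails. The chance of making both claims is about 75 to 82% (assumed correlation 0 to 0.9), against the stated 87% for remission tested alone. A 2.5% split would also hold the overall error at 5%, but it would lower primary power to about 78%, so the fixed sequence is preferable here.

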Also in the last case confidentiality of study subjects will be maintained as coupling of data bases will only be done by healthdata.be (TARDIS) as a third trusted party.

Trial documentation and archiving

Trial documentation will be provided electronically except for the site-specific logs (patient log, DoA, signature pages and signed ICF's). Source data are part of the patient medical file. Documentation will be kept for at least 20 years. Archiving at the end of the trial will be organized by the sponsor and done centrally.

Authorisation of participating sites

Centers will be selected and authorized based on a formal feasibility visit performed by the sponsor, CI and a representative of the CRO appointed by KCE (Harmony).

Required documentation

All the local documentation required prior to initiating a participating site should be collected in an Investigator Site File.

The Investigator Site File contains all essential documents held by Investigator(s) conducting a study, which individually and collectively permit the evaluation of the conduct of a study and the quality of the data produced.

For a list of all essential documents for the conduct of a clinical study, see ICH-GCP section 8. In this trial all documentation is kept on the e-platform except for the DoA, the patients identification list and the signed ICF's. These last documents will be kept separate in a binder on site.

Procedure for initiating/opening a new site

Pre-Trial Visit

After IEC approval of a study, before the start of recruitment, monitoring starts with a preliminary meeting with the PI and /or the sub investigator(s). The study team is informed about all aspects related to the organization of the study (Investigator Site File (ISF), CRF, facilities, study medication.) in accordance with GCP. Information on how to organize an ISF as well as template log forms covering items like adverse event reporting, drug accountability, patient screening and identification, etc....are provided

Site Initiation Visit

During the Site Initiating Visit (SIV), a first detailed review of all available documents in the ISF, essential to conduct a clinical study, will take place and study team is informed about all aspects related to the organization of the study.

Principal Investigator responsibilities

The local investigator is responsible to implement and conduct the trial in compliance with the approved protocol and will adhere to the principles outlined in the requirements for the conduct of clinical trials in the EU as provided for in " Directive 2001/20/EC" and any subsequent amendments, GCP guidelines, the Belgian law of May 7th 2004 regarding experiments on the human person, the Sponsor's SOPs, and other regulatory requirements as amended.

The local investigator is bound to confidentiality and will ensure that the confidential information contained in this document will not be used for any other purpose other than the evaluation or conduct of the clinical investigation.

Except where the investigator's signature is specifically required, it is understood that the term "investigator" as used in this protocol and protocol related documents refers to the investigators and/or appropriate study personnel that the investigators designates to perform a certain duty. The investigator is ultimately responsible for the conduct of all aspects of the study.

The organizing center, Department of Rheumatology of the University Hospitals Leuven, will provide notification to the investigators of protocol and amendment approvals by regulatory authorities, if applicable.

Schedule of Procedures

	Screen	Bl	W4	W8	(W12)	W16	(W20)	W24	(W28)	W32	(W35)	W40	(W44)	(W48)	W52	(W56)	W64	(W68)	W78	(W82)	W91	(W95)	W104	
Informed consent	x																							
Inclusion/Exclusion criteria	x																							
Demographic data	x																							
Medical history	x																							
Assessment of comorbidities	x									x		x	x	x	x	x	x	x	x	x	x	x	x	
Clinical/rheumatological examination	x	x	x	x	x	x	x	x	x	x	x	x	x	x	x	x	x	x	x	x	x	x	x	
RF and ACPA status	x	x	x	x	x	x	x	x	x	x	x	x	x	x	x	x	x	x	x	x	x	x	x	
ESR/CRP	x	x	x	x	x	x	x	x	x	x	x	x	x	x	x	x	x	x	x	x	x	x	x	
TB screening*	x																							
X-Ray/hands/feet	x								x								x						x	
DAS28-CRP/ESR	x	x	x	x	x	x	x	x	x	x	x	x	x	x	x	x	x	x	x	x	x	x	x	
PRO's**	x	x	x	x	x	x	x	x	x	x	x	x	x	x	x	x	x	x	x	x	x	x	x	
Employment status	x	x	x	x	x	x	x	x	x	x	x	x	x	x	x	x	x	x	x	x	x	x	x	
Randomization procedure						(x)	(x)	(x)	(x)	(x)	(x)	(x)	(x)	(x)										
Relevant concomitant medication	x	x	x	x	x	x	x	x	x	x	x	x	x	x	x	x	x	x	x	x	x	x	x	
(S)AE's and (S)AE's of interest	x	x	x	x	x	x	x	x	x	x	x	x	x	x	x	x	x	x	x	x	x	x	x	

(x) Optional

* According to local guidelines, to be repeated in case of starting bdMARD beyond 6 months after initial testing

** PRO's: HAQ, VAS scales done in routine; RAID, EQ5D, WPAI, PASS added to evaluate disease specific activity, health economics and patient acceptance, total duration of PRO collection about 10 min.

Flowchart	Screen	Bl	W4	W8	w12	W16	w20	w24	w28	w32	w36	w40	w44	w48	w52	w56	w60	w64
Randomized at W8	x	x	x	x	x	x	x	x	x	x	x	x	x	x	x	x	x	x
Randomized at W16	x	x	x	x	x	x	x	x	x	x	x	x	x	x	x	x	x	x
Randomized at W24	x	x	x	x	x	x	x	x	x	x	x	x	x	x	x	x	x	x
Randomized at W32	x	x	x	x	x	x	x	x	x	x	x	x	x	x	x	x	x	x
Not randomized	x	x	x	x	x	x	x	x	x	x	x	x	x	x	x	x	x	x

General mandatory visit	R+28w
General optional visit	

Mandatory visits for randomized patients	R+24w
	R+16w
	R+8w

Safety Reporting Flow Chart

To be developed based on the final protocol and what is described previously.

Amendment History

Amendment No.	Protocol version no.	Date issued	Author(s) of changes	Details of changes made
0	0.1	17/12/2016	JJ	First draft
0	0.2	02/01/2017	JJ	Second draft with implementation of remarks KCE and CTC
0	0.3	05/01/2017	JJ	Draft after internal discussion RW, JJ and SP
0	0.4	11/01/2017	JJ	Draft after remarks with PV VS SP JJ and AH (CTC)
0	0.5	13/01/2017	JJ	Incorporating remarks PV, VS, PS and JJ
0	0.6	19/01/2017	JJ	update
0	0.7	27/01/2017	JJ	Pre Final draft
0	0.8	31/01/2017	JJ	Final Draft
0	0.9	04/04/2017	JJ	Implementations of remarks KCE, statistical plan included (PV, VS, SP)
0	1.0	05/05/2017	SP, VS, JJ, PV, BVC	Further implementations of remarks KCE, statistical plan included (PV, VS, SP, BVC)
0	1.1	31/07/2017	JJ, SP, VS, KVE, PV	Implementation of remarks KCE
0	1.2	31/07/2017	JJ, SP, VS, KVE, PV	Internal revision Rheumatology
0	1.3	04/09/2017	JJ, PV, KCE	Implementation of remarks KCE
0	1.4	22/09/2017	JJ	Pre-final
0	1.5	30/10/2017	JJ, PV	Revision of the UZ Leuven team
0	1.6	20/11/2017	JJ, PV	Implementation of remarks KCE
0	1.7	14/12/2017	JJ, PV, CTC	Implementation of remarks on Pharmacovigilance (CTC) and economic evaluation
0	1.8	19/12/2017	JJ, PV, CTC	Review
0	1.9	02/01/2018	JJ	
0	2.0	09/01/2018	JJ, PV	Pre final review
0	2.1	11/01/2018	JJ, PV	Final review
0	2.2	25/01/2018	RW, JJ, PV	Final protocol
0	2.3	06/02/2018	JJ	Correction of typo's

0	2.4	26/04/2018	JJ	Information added on request of FAGG/EC
SM001	2.4	26/04/2018	NA	Addition of 5 sites, no adaptations made to the protocol.
SM002	2.4	26/04/2018	NA	Addition of 5 sites, no adaptations made to the protocol.
SM003	2.4	26/04/2018	NA	Addition of 1 site, no adaptation made to the protocol.
Non-SM1	3.0	16/07/2019	DB, JJ, PV	Non substantial amendment: Clarifications on the protocol and correction of typo's
SM004	4.0	18/03/2020	JJ, DB, PV, CL	Addition of procedures to be used in case of restrictions of regular outpatient visits due to governmental/local regulations (e.g. COVID-19 pandemic)
Non-SM2	4.1	29/04/2020	JJ	Clarifications on the protocol and correction of typo's

Reason for non-substantial amendment 1 (non-SM1) protocol version 3.0 16/07/2019.

The amendment is used to correct some typo's and for implementing clarifications on:

- The use of non-oral GC's before baseline: besides IA corticosteroids also IM and IV corticosteroids are not allowed within 4 weeks prior to baseline.
- The interpretation of the treat to target principle after w32
- The start-up schedule of Methotrexate
- Mandatory and optional visits
- Relevant medication
- Reportable (S)AE's

This protocol amendment does not change any procedure nor raise any possible new safety issues to patients and so only consists of clarifications to the protocol.

After discussion with our TSMC, this protocol amendment is considered as non-substantial.

Reason for substantial amendment 4 (SM004) protocol version 4.0 18/03/2020.

The amendment is used to add procedures to be used during the course of the COVID-19 outbreak, as government and hospital guidelines are limiting patient contacts when not assessed as essential.

This protocol amendment does meet the criteria to be substantial.

Reason for non-substantial amendment 2 (non-SM2) protocol version 4.1 dd 29/04/2020.

The amendment is used to correct some typo's and to add the restart of the screening of which a notification is sent to the FAGG/EC.

This protocol amendment is considered as non-substantial.
